- 2) Assess the preliminary impact of an alcohol-focused brief intervention on reducing alcohol consumption among a sample of hazardous drinking, PrEP-prescribed MSM.
- 3) Assess the preliminary impact of an alcohol-focused brief intervention on improving PrEP adherence and retention in PrEP-related care among a sample of hazardous drinking, PrEP-prescribed MSM.
- 4) Assess the preliminary impact of an alcohol-focused brief intervention on reducing condomless sex and STIs among a sample of hazardous drinking, PrEP-prescribed MSM.

IV. Study Design

We will conduct a pilot randomized controlled trial (RCT) of an alcohol-focused brief intervention with supplementary modules that focus on concurrent substance use and depression.

A total of 120 PrEP-prescribed MSM who are hazardous drinkers will be recruited from two medical clinics, Toronto General Hospital (TGH) and Maple Leaf Medical Clinic (MLMC), located in downtown Toronto. Participants will be randomly assigned to either the intervention condition or treatment as usual (TAU) based on a 2:1 intervention:TAU ratio. All participants will complete biological and behavioral measures at baseline and at 3- and 6-months post-baseline to assess PrEP-related behaviors, alcohol consumption, substance use, and depression. An overview of the trial design is depicted in Figure 1.

Figure 1. Pilot RCT design overview.

Eligibility Criteria

To be included in the study, participants must be (a) aged 18 years or older, (b) be a patient of TGH or MLMC, (c) be a man who identifies as a gay or bisexual, and/or a man who has sex with other men, (d) have been prescribed PrEP for at least 3 months, and (e) meet the criteria for hazardous drinking, (i.e., based on a score of ≥ 4 on the Alcohol Use Disorders Identification Test – Consumption measures (AUDIT-C))²⁰

Participants will be excluded if they do not meet all of the above-mentioned inclusion criteria.

Study Procedures and Measures

Men presenting for routine PrEP-related care at TGH and MLMC will be made aware of the study either through TGH/MLMC clinic staff members (e.g., doctors, nurses, clinic research staff) or via study information cards and/or posters (see “Recruitment Ad” attachment) at their respective clinics. Interested individuals will be referred to a CAMH research staff member. The CAMH research staff member will provide additional information about the study (see “Pre-Screening Script” attachment) and answer any questions that the individual may have.

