Individuals who indicate that they would like to participate will complete either a brief, self-administered tablet-based eligibility screener or an over-the-phone screener (see “Pre-Screening Questionnaire” attachment), and qualifying individuals will be offered participation and asked to provide informed written consent (see “Consent Form” attachment). Potential participants will be encouraged to take as much time as they need to review the information and only give consent when they are ready to participate. The study comprises of a baseline session, and two follow-up visits at 3- and 6- months post initial visit. Designated CAMH staff members will conduct and oversee all study procedures.

Pre-Screening

A CAMH research staff member will introduce the study to the potential participant using the pre-screening script (see “Pre-Screening Script” attachment). Individuals interested to take part in the study will complete an eligibility pre-screening questionnaire (see “Pre-Screening Questionnaire” attachment) Pre-screening will take approximately 5 minutes to complete and will be conducted over the phone or in person. Questions in the screener ask participants about their age, time on PrEP, sexual orientation, and alcohol consumption patterns.

Baseline Session

During their baseline session, participants will provide samples of dried blood spots (DBS) via finger prick (see “Dried Blood Spot Testing” below and “Dried Blood Spot” attachment) and complete a self-administered tablet-based survey. The survey, which is based on the previously-approved survey that was employed in the first phase of this project (CAMH REB# 101/2017; UHN REB#18-5014), will include measures assessing PrEP-related behaviors and other key factors including alcohol use, substance use, and depression (see “Measures” below and the “Survey” attachment). Upon completion of the survey, the tablet-based program will randomly assign participants to either the intervention condition or TAU based on a 2:1 intervention:TAU ratio. Intervention condition participants will receive a one-time, alcohol-focused brief behavioural personalized feedback intervention delivered seamlessly on the same tablet, which will also embed supplementary modules focused on substance use and depression when necessary (see “Intervention” below and the “Intervention” attachment).

Intervention

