like to receive an electronic copy of their personalized drinking feedback report and/or a list of local services for mental health- and substance-related concerns. Providing an email address will be completely voluntary. All email addresses collected will be deleted after the data have been downloaded to the CAMH secure server. To ensure participants are aware that their email address will be connected to their data, we have included the following text in the consent form: “It is recommended that for the report, you use an email address that does not identify you (for example, that you use an email that does not include your first or last name or other information that could identify you). This is because the email address you provide for the report will be temporarily stored in a secure Qualtrics database and will be connected with your data. If you use identifiable information in your email, the Qualtrics database may be able to link you to the data you provide (i.e., your data will be identifiable in the Qualtrics database). The choice is yours, and the research team would like to make you aware of this.” TAU participants will receive no intervention.

Follow Up Sessions

At 3-month and 6-month follow-up visits, all participants will complete similar questionnaires to the baseline survey/screener measuring the same constructs in order to identify any changes in outcomes over time. DBS samples from finger prick will also be obtained at these follow up visits to test PrEP adherence and alcohol use biomarkers (see “Dried Blood Spot Testing” and “Measures” below, as well as the corresponding attachments). For participants in the intervention arm only, an additional questionnaire will be included at the end of the 6-month assessment to evaluate the perceived acceptability of the intervention (included in the “Survey” attachment). With participants’ explicit written consent, retrospective chart reviews will be conducted by CAMH research staff for aspects pertaining to PrEP treatment-related factors; alcohol, substance use, and mental health-related aspects; incident STIs; and other relevant clinical indicators (see “Chart Review” attachment). Chart review items were previously approved in the first phase of this study (CAMH REB# 101/2017-03; UHN REB# 18-5014.3).

Dried Blood Spot Testing

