PrEP adherence. Adherence to PrEP will be assessed at baseline, 3-months, and 6-months using a combination of behavioral and biological assessments to evaluate the adherence-focused component of **Specific Aim 3**. The behavioral assessment will be comprised of adapted versions of two well-validated measures of adherence,^{43,44} identifying 1) the number of missed PrEP doses over the past seven days; and 2) the percent of PrEP doses taken over the past four weeks. These measures have been employed in a number of intervention trials and provide good estimates of adherence.⁴⁵ For both measures, suboptimal adherence will be defined as taking <80% of one's prescribed PrEP doses.¹¹ DBS samples obtained at baseline, 3-, and 6-months will be analyzed for quantities of PrEP components (e.g., tenofovir/emtricitabine (TFV/FTC)), using a validated liquid chromatography tandem mass spectrometry method widely used in PrEP research.^{6,9,46-55} The half-life of TFV is 15 hours and that of FTC is 10 hours⁵⁰ which will allow the quantification of recent use of PrEP with a single DBS sample. Furthermore, blood plasma has been shown to provide a good indication of PrEP use for periods ranging from 24 hours to seven days.^{50,51,54} A cut off for the concentration of ≤ 10 ng/ml (for either TFV or FTC) will be employed, as this has been shown to be indicative of inconsistent PrEP intake.^{50,51}

Retention in care. **Specific Aim 3** includes an additional focus on retention in PrEP-related care. Attendance at clinic visits that correspond with 3- and 6-month assessments, and attendance during any other regularly scheduled PrEP clinic visits during the 6-month follow-up period, will be used as an indicator of retention.

Engagement in condomless sex. In accordance with **Specific Aim 4**, condomless sex will be assessed at baseline and follow-up study visits using an adapted version of a validated MSM-focused sexual behavior assessment that queries condom use during the past three months.⁵⁶ Responses at each time point will be dichotomized to identify participants who engaged in any condomless anal sex. As an objective indicator of condomless sex, incident chlamydia, gonorrhea, syphilis, and HCV, diagnosed at each time point, will be identified through chart extraction.

Additional Measures

Participant characteristics. Demographic factors to be collected include age, race, educational background, and income. These factors will be queried during the baseline assessment.

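### Retention in PrEP care has no pre-specified baseline attendance measure or covariate, so its between-arm comparison gives up some precision that the planned chart review could recover (minor)

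*Combined protocol and SAP*

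**What the plan says.** Under Outcome Measures, Retention in care, the outcome has two parts. The first is "Attendance at clinic visits that correspond with 3- and 6-month assessments". The second extends this to the remaining appointments: "attendance during any other regularly scheduled PrEP clinic visits during the 6-month follow-up period, will be used as an indicator of retention". Both lie after the baseline session.

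The neighbouring outcomes are handled differently. The alcohol measures (AUDIT, two drinking items, PEth), PrEP adherence (self-report and dried blood spot) and condomless sex are each stated to be measured at baseline as well as at 3 and 6 months. STIs come from charts at each time point; that probably includes baseline, but calling them *incident* leaves it open.

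On recruitment, "Men presenting for routine PrEP-related care at TGH and MLMC will be made aware of the study", and eligibility requires that a man "have been prescribed PrEP for at least 3 months". On allocation, "the tablet-based program will randomly assign participants to either the intervention condition or TAU", with two men in the intervention arm for each one in TAU; no stratification is stated. Statistical analyses gives mixed models with a random intercept per patient for Aims 2 to 4 and names no covariates. Under Follow Up Sessions, with written consent, "retrospective chart reviews will be conducted by CAMH research staff for aspects pertaining to PrEP treatment-related factors"; the text names neither prior visit attendance nor a look-back period.

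**The concern.** Aim 3 speaks of improving retention, and Study Design says that measures at baseline and follow-up will assess PrEP-related behaviours, a term under which the introduction places retention in care. Yet this outcome has no starting value. The enrolment visit cannot supply one: men are approached when they come for care, so attendance at that visit is nearly uniform.

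Past attendance is a plausible predictor of later attendance, although the documents give no figure for the link. If it does predict, leaving it out of the model keeps explainable between-man variation in the error. A chance difference between arms in prior attendance then also passes into the retention comparison uncorrected. The other outcomes bring a baseline observation that can enter the mixed model; retention brings follow-up data only.

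**Working it through.** The plan states no figure for retention (its power paragraph concerns adherence), so there is nothing to reproduce.

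**Inputs from the documents.** "A total of 120 PrEP-prescribed MSM who are hazardous drinkers will be recruited from two medical clinics", allocated 2:1, hence 80 and 40 men.

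**Assumed inputs.** Share of poor prior attenders p = 20–40%, with 10% as a low case. Later retention 90% in good and 50–60% in poor prior attenders, a gap g of 0.30–0.40. No intervention effect, no dropout, two-sided 5% level.

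**1. Chance imbalance.** Let X₁ ~ Bin(80, p) and X₂ ~ Bin(40, p) be independent. Exact probabilities for |X₁/80 − X₂/40|:

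| p | 10 points or more | 15 points or more |
|---|---|---|
| 0.10 | 0.10 | 0.01 |
| 0.20 | 0.23 | 0.06 |
| 0.30 | 0.29 | 0.10 |
| 0.40 | 0.32 | 0.13 |

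**2. Shift in the retention difference, given an imbalance.** Shift = imbalance × g. This runs from 0.10 × 0.30 = 3 points to 0.15 × 0.40 = 6 points, in either direction.

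**3. Compared with ordinary sampling error.** Overall retention R = 0.90 − p·g, and SE = √[R(1 − R)(1/80 + 1/40)] = √[R(1 − R) × 0.0375].
- p = 0.20, g = 0.30: R = 0.84, SE = √(0.1344 × 0.0375) = 7.1 points.
- p = 0.40, g = 0.40: R = 0.74, SE = √(0.1924 × 0.0375) = 8.5 points.

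A 3–6 point shift is therefore below one SE (3/7.1 = 0.42; 6/8.5 = 0.71).

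**4. Variance removed by adjustment** (linear approximation). Share = p(1 − p)g² / [R(1 − R)].
- p = 0.20, g = 0.30: 0.0144/0.1344 = 11%. The 95% half-width falls from 1.96 × 7.1 = 13.9 to 13.9 × √0.893 = 13.1 points.
- p = 0.40, g = 0.40: 0.0384/0.1924 = 20%. The half-width falls from 16.6 to 16.6 × √0.80 = 14.9 points.
- p = 0.10: 0.0081/0.1131 = 7% (g = 0.30) to 0.0144/0.1204 = 12% (g = 0.40).

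In unadjusted sample size, 11–20% corresponds to about 120/0.893 = 134 to 120/0.80 = 150 men. These figures assume that prior attendance is classified without error.

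**5. Type I error.** In a simulation with correlation r = 0.5 between prior and later attendance, the unadjusted test rejects in 4.9% of null trials, so it is valid overall. Given an imbalance of 1.96 SE, its conditional error is 0.079 at r = 0.3 and 0.129 at r = 0.5. The assumptions in step 4 imply r = √0.107 = 0.33 to √0.20 = 0.45.

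**The case against.** The strongest reply is that a randomised comparison needs no baseline. The plan tests whether the intervention arm does better at both follow-up points, and TAU supplies the reference for improvement. Retention is by nature a post-entry outcome. This stands: the comparison is valid without the covariate, and the ordinary confidence interval already covers the 3–6 point shift.

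A reader might infer that recruiting men as they attend makes the arms differ, or biases the comparison. The documents do not support that. This route selects attenders into both arms alike before randomisation; it bears on ceiling effects and generalisability. Only chance imbalance remains.

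A reader might also infer that retention is the only Aim 2–4 outcome without a baseline, or that no prior-attendance data will exist. Neither is established. The STI wording is ambiguous. Retention in care is listed among the previously approved behavioural measures, and the Survey and Chart Review attachments are not available here, so an item may already be collected. What can be said is that the written plan defines none as a baseline value or covariate. Equally, that the charts record past visits is an inference, though a fair one, since the outcome itself requires clinic attendance to be ascertainable.

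Finally, the gain may be less than calculated. Eligibility guarantees only 3 months on PrEP, which may mean one or two visits, possibly including the recruitment visit. Recruiting attenders also makes a low share of poor attenders plausible. Both points stand.

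**Conclusion.** The point holds as a minor one. Retention is defined from follow-up attendance alone, and the plan pre-specifies no baseline attendance measure or covariate for it. The cost is lost precision and exposure to chance imbalance, not a design bias. The size rests entirely on assumed attendance and retention rates. At 20–40% poor prior attenders, the 95% half-width would narrow by roughly 1 to 2 points; near ceiling, or with one or two prior visits per man, by less. The trial is a pilot that the protocol calls a feasibility study, and retention is one component of Aim 3, so nothing in the main conclusions turns on this.

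**What to change.** In the chart review already planned and consented, extract the PrEP visits scheduled and attended in a fixed window before the baseline session, excluding the recruitment visit. The window could reach back up to 6 months, and should cover at least the 3 months on PrEP that eligibility guarantees. Pre-specify the proportion attended, together with time on PrEP, as baseline covariates in the retention model, and state how men with no scheduled visit in the window are coded. If the Survey or Chart Review form already captures prior attendance, only the analysis text needs to change.

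The cost is a few chart fields and two model terms, with no extra visits. The downside is that men with short PrEP histories contribute little information, so the gain may be small.

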Substance use and Depression. Substance use other than alcohol will be assessed using the National Institute on Drug Abuse (NIDA) - Modified Assist Screening Tool (NIDA M-ASSIST).⁵⁷ This measure queries lifetime use of a variety of substances, frequency of substance use during the past three months, and negative consequences experienced as a result of substance use. Participants will be identified as possessing a potential substance use issue based on NIDA M-ASSIST scoring. Participants will complete the Center for Epidemiologic Studies Depression Scale-10 (CESD-10).⁵⁸ A score ≥ 10 will be used as an indicator of the presence of marked depressive symptomatology.⁵⁸ Both measures will be administered at baseline and at the two follow-up time points.

It should be noted that the demographic and behavioral measures (i.e. alcohol consumption, PrEP adherence, retention in care and engagement in condomless sex) included in this study were previously approved in the first phase of this study (CAMH REB# 101/2017-02; UHN REB# 18-5014).

Data Analysis

Statistical power. As this is a feasibility study and not intended as a definitive clinical trial, sample size considerations focus on expected effect sizes detectable with the design. The following effect size for the variable that likely has the least power (i.e., adherence –**Aim 3**) can be detected based on the following assumptions: there is a combined effect of 1) the suggested alcohol intervention on alcohol intake,⁵⁹ and 2) the effect of lowered alcohol intake on PrEP adherence.¹¹ Suboptimal PrEP adherence, defined as taking $<80\%$ of all doses, was estimated based on the literature¹¹ and assumed to be 30% among heavy alcohol users.⁸ With the current sample size, we would be able to significantly detect Odds Ratios of 3 and higher, and assuming confounding with an R^2 of other variables on the dependent variable, Odds Ratios of 3.5 and higher. We will be able to detect differences in proportions of about 20% with a 95% Confidence Interval between 2% and 28%.⁶⁰ Other factors in **Aims 2, 3, and 4** can detect smaller effect sizes.

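### The self-reported condomless-sex outcome is coded any versus none over three months, so it cannot show a reduction short of stopping, which is part of what Aim 4 sets out to assess

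*Combined protocol and SAP*

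**What the plan says.** Section III, Aim 4, is to assess the preliminary impact of an alcohol-focused "brief intervention on reducing condomless sex and STIs among a sample of hazardous drinking, PrEP-prescribed MSM".

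Under Outcome Measures, Engagement in condomless sex, the self-report instrument "queries condom use during the past three months". The rule for using it is: "Responses at each time point will be dichotomized to identify participants who engaged in any condomless anal sex". No count, proportion or partner-level outcome is named, and no reason is given for the cut.

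The next sentence adds a second Aim 4 outcome: "As an objective indicator of condomless sex, incident chlamydia, gonorrhea, syphilis, and HCV, diagnosed at each time point, will be identified through chart extraction".

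Under Data Analysis, the power paragraph works from suboptimal adherence, "assumed to be 30% among heavy alcohol users", and gives a detectable odds ratio of 3 (3.5 allowing for confounding). It treats adherence as probably the least powered variable and says the other factors in Aims 2, 3 and 4 can detect smaller effects. It gives no rate for condomless sex. Aims 2 to 4 are to be tested with generalized linear mixed models with a random intercept per patient.

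**The concern.** The aim is worded as a reduction, while the coding records only whether there was any act in three months. A change from many acts to few leaves the coded value the same. The mismatch can be seen from the text alone and needs no prevalence figure.

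The intervention is a single tablet session giving feedback on drinking, and any effect on sexual behaviour is expected to come through lower alcohol intake. Partial change is a plausible result of that route. If it occurs, the self-report analysis could show little or nothing, and a pilot meant to guide later work would pass on a misleading null for that outcome. The alcohol outcomes, by contrast, keep two quantity items.

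**Working it through.** **Inputs from the plan.** "A total of 120 PrEP-prescribed MSM who are hazardous drinkers will be recruited from two medical clinics", allocated "based on a 2:1 intervention:TAU ratio": 120 × 2/3 = 80 intervention and 120 × 1/3 = 40 TAU. Recall window three months. Two-sided 5% is inferred from the 95% interval in the power paragraph.

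**Assumed, because the plan does not say.** 80% as target power; TAU prevalence of any condomless sex 50-95%; mean acts 1 to 12 per three months; negative-binomial counts with dispersion k = 1; one follow-up, no dropout, no baseline adjustment.

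**Step 1. The plan's own figure.** Pooled two-proportion test, with p̄ the pooled proportion:

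power = Φ{ [|p₁−p₂| − 1.96·√(p̄(1−p̄)(1/40+1/80))] / √(p₁(1−p₁)/40 + p₂(1−p₂)/80) }

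- From 30%, OR 3 downward: odds 0.4286/3 = 0.1429, or 12.5%. Power 64%.
- From 30%, OR 3 upward: odds 1.286, or 56%. Power 79%.

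So OR 3 corresponds to about 80% power only in the upward direction. For a fall in suboptimal adherence, the same formula reaches 80% power at 30% to 9.3%, an OR of (0.30/0.70)/(0.093/0.907) ≈ 4.2.

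**Step 2. What any/none needs for 80% power, 40 v 80.**

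| TAU any | Must fall to | OR |
|---|---|---|
| 50% | 24% | 3.1 |
| 60% | 33% | 3.0 |
| 70% | 43% | 3.1 |
| 80% | 55% | 3.3 |
| 90% | 68% | 4.3 |
| 95% | 75% | 6.2 |

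**Step 3. What halving the acts does to any/none.** For a negative binomial with mean m, P(any) = 1 − (k/(k+m))^k. With k = 1 this is m/(1+m), so the odds of any equal m. Halving m therefore halves the odds: OR 2 at every mean, well short of the values in Step 2.

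Example, mean 8 to 4: P(any) = 8/9 = 0.889 and 4/5 = 0.800. p̄ = (40×0.889 + 80×0.800)/120 = 0.830. The first root is √(0.830×0.170×0.0375) = 0.0728, and 1.96 times that is 0.143. The denominator is √(0.00247 + 0.00200) = 0.0669. Power = Φ((0.089 − 0.143)/0.0669) = Φ(−0.81) ≈ 21%.

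**Step 4. Any/none against the counts, by simulation** (z-test on any/none, rank-sum test on counts):

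| Scenario | Any: TAU → intervention | Power, any/none | Power, counts |
|---|---|---|---|
| 50% fewer acts, mean 4 | 80% → 67% | about 33% | about 74% |
| 50% fewer acts, mean 8 | 89% → 80% | about 20% | about 79% |
| 50% fewer acts, mean 12 | 92% → 86% | about 15% | about 81% |
| 50% fewer acts, mean 1 | 50% → 33% | about 42% | about 53% |
| 20% stop, others 30% fewer, mean 8 | 89% → 68% or a little lower | about 75% | about 82% |
| 30% stop, others unchanged, mean 8 | 89% → 62% | about 90% | about 69% |

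In the last row, 0.889 × 0.70 = 0.622. In the row above it, the 80% who do not stop have mean 0.7 × 8 = 5.6, so P(any) = 0.80 × 5.6/6.6 = 0.68. For the three halving scenarios at means 4 to 12, grouping the counts into four ordered bands (0, 1-3, 4-9, 10 or more) still gives roughly 70-76%, so most of the gain remains if the survey records only frequency bands.

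**The case against.** **Aim 4 as a whole.** A reader might infer that Aim 4 can register only complete cessation. The documents do not support that. Incident STIs from charts are a separate Aim 4 outcome that does not depend on the cut and can change when men reduce without stopping. The any/none item also registers men who start, or who avoid starting. The limit belongs to the self-report measure alone, although STI diagnoses do not replace the behavioural detail that is discarded.

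**Size of the loss.** A reader might also infer that most of the power is lost. That follows only if every man's acts fall by a similar proportion at a fairly high frequency. The plan states no prevalence, frequency or form of effect. At low frequency, or when some men stop and others cut down, the loss is small; under pure cessation any/none is the better analysis. This objection stands, and it is the reason to keep any/none.

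**The comparison with adherence.** The ORs in Step 2 are set against the plan's stated 3. On the same formula a fall in adherence failure needs about 4.2, so on a like-for-like basis any/none is clearly worse only from a prevalence of about 90%.

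**The simulation is not the planned model.** It uses one follow-up and a rank test. Two follow-ups in a mixed model would raise power for both codings. The figures show the direction and rough size of the contrast only.

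**Availability and proportion.** The survey attachment is not shown. Dichotomizing implies that finer responses exist, but they may be categories and not counts. The trial is a feasibility pilot and any/none is simple and fixed in advance. These points limit the weight of the concern, but the plan still tests Aim 4 formally.

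**Conclusion.** The point holds for the self-reported condomless-sex outcome. It cannot register a reduction short of stopping, and no graded counterpart is planned, although the aim concerns reduction.

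The cost in power is conditional. Under a uniform 50% cut, with an assumed TAU mean of 4 to 12 acts and dispersion 1, it is roughly 15-33% against 74-81%. It is slight at a mean of one act and reverses under pure cessation.

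The statement that Aim 4 factors can detect smaller effects than adherence has no supporting rate for this outcome. Against the plan's stated OR of 3, it would not hold at a TAU prevalence of 80% or more, where 3.3 to 6.2 is needed on a single follow-up.

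**What to change.** 1. Keep any/none as defined. Pre-specify beside it a mixed-model analysis of the undichotomized responses with the same random intercept: negative binomial if the survey records acts or partners, ordinal if it records frequency categories.
2. Restrict the statement on smaller effect sizes so that it does not cover any/none condomless sex, unless an expected prevalence is given that supports it, with the detectable effect.

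The cost is analysis text, provided the survey already records graded responses; if it does not, the first change would mean altering the instrument. The downside is one more outcome, probably skewed, to model and interpret in a pilot.

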Statistical analyses. Analyses pertaining to feasibility and acceptability indicators (**Aim 1**) will be based on descriptive statistics involving frequency counts (e.g., intervention completion rates) and mean scores (i.e., acceptability measure). The anticipated patterns pertaining to **Aims 2, 3, and 4** will be tested with generalized linear mixed effect models including random intercepts for every patient,^{61,62} based on the expectation that the intervention group will have better outcomes at both follow-up time points. Mixed effect models have fewer assumptions compared to more

traditional repeated measures of analyses of variance⁶¹ with respect to missing values.^{63,64}

For the quantification of the causal impact of alcohol, we will additionally use path models, where alcohol consumption levels will be introduced into the equations, with the hypothesis that the introduction of this variable will make the differences between experimental and control groups disappear.

Reference List

1. Public Health Agency of Canada. (2015) HIV and AIDS in Canada: Surveillance Report to December 31, 2014. Ottawa: Minister of Public Works and Government Services Canada. Available at: <http://www.phac-aspc.gc.ca/aids-sida/publication/epi/2010/index-eng.php>. Accessed April 13 2017.
2. Public Health Agency of Canada. (2015) Summary: Estimates of HIV Incidence, Prevalence and Proportion Undiagnosed in Canada, 2014. Available at: <http://healthycanadians.gc.ca/publications/diseases-conditions-maladies-affections/hiv-aids-estimates-2014-vih-sida-estimations/index-eng.php>. Accessed April 13 2017.

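### Incident STIs are read from chart diagnoses with no record of who was tested, so an arm difference in clinic attendance could distort the Aim 4 STI comparison

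*Combined protocol and SAP*

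**What the plan says.** The STI outcome is defined in section IV, Outcome Measures, under Engagement in condomless sex. Alongside a self-reported measure of any condomless anal sex, the plan adds STIs "As an objective indicator of condomless sex": "incident chlamydia, gonorrhea, syphilis, and HCV, diagnosed at each time point, will be identified through chart extraction".

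Under Follow Up Sessions, the chart review is retrospective and covers, among other things, "incident STIs; and other relevant clinical indicators". Its item list is in a Chart Review attachment that is not part of the public document. The study's own follow-up specimens are dried blood spots: "DBS samples from finger prick will also be obtained at these follow up visits to test PrEP adherence and alcohol use biomarkers". No study STI test is described there or under Dried Blood Spot Testing.

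Aim 3 concerns "improving PrEP adherence and retention in PrEP-related care". Under Retention in care, the measure is "Attendance at clinic visits that correspond with 3- and 6-month assessments", and in addition "attendance during any other regularly scheduled PrEP clinic visits during the 6-month follow-up period, will be used as an indicator of retention".

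Under Statistical analyses, Aims 2 to 4 are tested with generalized linear mixed models with a random intercept per patient, on the expectation that "the intervention group will have better outcomes at both follow-up time points". The models are said to need fewer assumptions about missing values than repeated-measures analysis of variance. No adjustment for visits or tests is named.

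**The concern.** A diagnosis can appear in a chart only if the man was seen and tested. Because the trial does no STI testing itself, detection depends on clinic care, and attendance at that care is something the intervention is meant to improve. The plan therefore hypothesises more clinic attendance and fewer STI diagnoses in the same arm. If attendance brings testing with it, success on Aim 3 raises the chance of detection in the arm where Aim 4 predicts fewer infections.

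The planned model does not settle this. Its handling of missing values helps only if an untested interval is entered as missing. If the absence of a diagnosis is entered as no STI, nothing is missing as far as the model can tell.

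At stake is how the biological Aim 4 measure is read. A real reduction could look like no effect, or a null effect like harm, because of who was tested.

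**Working it through.** The plan states no STI rate, testing rate or STI power, so there is no figure of its own to reproduce. All rates below are assumptions.

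**Inputs from the plan.** 120 men randomised 2:1, hence 80 intervention and 40 TAU.

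**Assumed inputs.** True STI risk of 15% in TAU; true risk ratio (RR) of 1.00 or 0.80, so 15% or 12% in the intervention arm; several testing rates.

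**Model.** Suppose that untested men are counted as free of STI, that testing is unrelated to infection within each arm, and that an untested infection is never found later. Then, in each arm:

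observed risk = true risk × proportion tested

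observed RR = true RR × (intervention testing rate / TAU testing rate)

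The true risk cancels from the ratio, so the distortion does not depend on the STI rate.

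| True RR | Tested, TAU v intervention | Observed risk, TAU | Observed risk, intervention | Observed RR |
|---|---|---|---|---|
| 1.00 | 75% v 90% | 0.15 × 0.75 = 0.1125 | 0.15 × 0.90 = 0.135 | 1.20 |
| 0.80 | 75% v 90% | 0.1125 | 0.12 × 0.90 = 0.108 | 0.96 |
| 0.80 | 80% v 90% | 0.15 × 0.80 = 0.120 | 0.108 | 0.90 |
| 0.80 | 85% v 95% | 0.15 × 0.85 = 0.1275 | 0.12 × 0.95 = 0.114 | 0.89 |

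**When a benefit would reverse.** The observed RR exceeds 1 when the testing ratio exceeds 1 / true RR. For a true RR of 0.80 that is 1 / 0.80 = 1.25. At 75% v 90% the ratio is 0.90 / 0.75 = 1.20, so the benefit is nearly hidden but not reversed. At 70% v 95% the ratio is 1.36 and the observed RR is 0.80 × 1.36 = 1.09. With equal testing the observed RR equals the true RR.

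**Size in events.** With true RR 0.80 and 75% v 90% tested, expected diagnoses fall from 40 × 0.15 = 6.0 to 40 × 0.1125 = 4.5 in TAU, and from 80 × 0.12 = 9.6 to 80 × 0.108 = 8.6 in the intervention arm: about one event per arm.

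**Would analysing only tested men be enough?** Not by itself. Take a true risk of 15% in both arms and 90% of the intervention arm tested regardless of infection. In TAU, let 90% of infected and 72% of uninfected men be tested.

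- TAU tested: 0.15 × 0.90 + 0.85 × 0.72 = 0.135 + 0.612 = 0.747, or about 75%.
- Positives among tested: TAU 0.135 / 0.747 = 18.1%; intervention 0.135 / 0.90 = 15.0%. RR = 15.0 / 18.1 = 0.83, a spurious benefit.
- Untested counted as negative: 13.5% v 13.5%, RR 1.00, which is correct here.

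Each coding of untested men can therefore mislead, in opposite directions, depending on why men were tested.

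**Precision.** At an assumed 20% TAU risk and RR 0.80, power with 80 v 40 men, full testing and two-sided 0.05 is about 8%.

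**The case against.** The strongest reply has five parts.

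- **No rule is stated.** A reader might infer that the plan counts untested men as free of STI. It does not say so; untested intervals could be entered as missing, and the mixed models are chosen partly for their treatment of missing values. This stands: the handling is unspecified, and the distortion shown applies to one of the two readings. The other reading carries the tested-only risk shown in the working.
- **The chart form is unseen.** The Chart Review attachment may already collect tests done, dates and negative results. This stands, and if so the fix is cheaper. The outcome and analysis text still makes no use of such data.
- **The bias is conditional.** A reader might infer that the STI count in the intervention arm will rise and that the benefit will be reversed. The documents do not support that. Aim 3 assesses a preliminary impact on retention and does not establish one; that STI tests take place at PrEP visits is an inference; and reversal at a true RR of 0.80 needs a testing ratio above 1.25.
- **The model is simple.** Men with symptoms may attend whatever their arm, and an infection missed at 3 months may be found at 6 months. Either would shrink the distortion.
- **Little turns on it.** This is a pilot with very low power for STIs. Self-reported condomless sex is measured at every study visit without any STI test, and attendance is itself compared by arm, so a difference would be visible. This limits the severity. But visible attendance does not show who was tested for which infection, and even a descriptive estimate should not take its direction from testing.

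**Conclusion.** The point holds in conditional form. The chart-based STI indicator has no testing denominator in the outcome or analysis text and no rule for untested intervals. If the intervention raises attendance, if that raises testing, and if no diagnosis is read as no STI, the comparison is biased against the intervention by the ratio of testing rates. Under assumed testing of 75% v 90%, that multiplies the risk ratio by 1.20; under 80% v 90%, by 1.125; under equal testing, not at all. These figures rest on assumed rates and on testing being unrelated to infection. The severity is low, because the comparison can only be descriptive at this sample size. It is still worth correcting, because the change is small and would help prevent a testing difference from being read as an STI effect.

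**What to change.** 1. In the planned chart review, record for each of the four infections and each interval (baseline to 3 months, 3 to 6 months) whether a test was done, as well as its result. If the attachment already captures this, only the analysis text needs to change.
2. Report testing rates by arm, infection and interval.
3. Present the STI comparison in two ways: untested intervals set to missing (positives among those tested), and untested intervals counted as negative. Claim an STI effect only if the two agree.
4. State beside the results that neither analysis is unbiased alone. Testing happens after randomisation, and if infected men are more likely to be tested, the tested-only analysis can favour the intervention.

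The cost is a few extraction fields, one added analysis and a short addition to the analysis text. Recruitment, visits and care do not change, and because the chart review is retrospective the fields can be added at any time before extraction.
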